## Appendix II Visit Schedule

Appendix II A - Visit Schedule - Groups 1A-1C - **HEALTHY PARTICIPANTS**

Version: V04\_0 01-APR-2021

Visit	1	2	3	4	5	6	7	8	9	10	11
Study Week	Screen	Wk 0				Wk 1	Wk 2	Wk 3	Wk 4	Wk 8	Wk 13
Study Day	D-7 to D-1	D 0	D 1	D 3	D 5 	D 7	D 14	D 21	D 28	D 56	D 90
Visit Window (+/- days)	-	-	-	1	1	1	2	3	3	4	7
Eligibility and History											
Informed Consent	x										
Inclusion/Exclusion criteria	x										
Demographics	x										
Medical History	x	x	x	x	x	x	x	x	x	x	x
Concomitant Medication	x	x	x	x	x	x	x	x	x	x	x
Study Intervention											
In-Patient Admission		x									
DZIF-10c Inhalation		x									
Study Procedure											
ECG	x										
AESI / Inhalation-related reactions	x	x	x	x	x	x					
Adverse Events	x	x	x	x	x	x	x	x	x	x	x
General Physical	x										
Directed Physical 	x	x	x	x	x	x	x	x	x	x	x
Vital Signs 	x	x 	x	x	x	x	x	x	x	x	x
Weight	x								x		x
Height	x										
Pregnancy counseling	x										
Pregnancy testing in women of childbearing potential	x	x 					x		x	x	x
Pulmonary function testing	x	x 	x			x			x		x
Biosamples											
Virology screening labs  (Local lab)	x										
Safety lab  (Local lab)	x	x	x	x	x	x	x		x	x	x
Coagulation parameters (INR, PTT) (Local lab)	x										
Urinalysis 	x					x			x		x
SARS-CoV-2 antibody serology  (Local lab)	x	x									
PK samples (Central lab)		x 	x	x	x	x	x	x	x	x	x
Naso- or Oropharyngeal SARS-CoV-2 swab (Local lab) 	x	x 				x					
Anti-DZIF-10c antibody (ADA) assay sample (Central lab)		x					x		x	x	x
Research lab (PBMCs) (Central lab)		x							x		x

1. Optional visit.

2. Symptom-oriented examination.

3. Vital signs: Heart rate, systolic/diastolic blood pressure, temperature, respiratory rate, SpO2 (pulse oximetry).

4. Vital signs determined prior to inhalation, at the end of the inhalation, 1 h (+/- 10 min) post end of inhalation, and 4 h (+/- 15 min) post end of inhalation.

5. Negative serum or dipstick urine b-HCG from sample obtained on day of infusion must be available prior to the start of the administration.

6. Pulmonary function testing to be performed prior to inhalation, 30 min (+/- 5 min) post end of inhalation, and 4 h (+/- 15 min post end of inhalation).

Parameters: FEV1, FVC, FEV1/FVC, VC, IVC, PEF, PIF.

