Appendix II B - Visit Schedule - Groups 2A-2D - **SARS-CoV-2-INFECTED PARTICIPANTS**

Version: V04\_0 01-APR-2021

Visit	1	2	3	4	5	6	7	8	9	10	11
Study Week	Screen 	Wk 0				Wk 1		Wk 2	Wk 4	Wk 8	Wk 13
Study Day	D-3 to D 0	D 0	D 1	D 3	D5 	D 7	D10 	D 14	D 28	D 56	D 90
Visit Window (+/- days)	-	-	-	1	1	1	1	2	3	4	7
Eligibility and History											
Informed Consent	x										
Inclusion/Exclusion criteria	x										
Demographics/Medical History	x										
Medical History	x	x	x	x	x	x	x	x	x	x	x
Concomitant Medication	x	x	x	x	x	x	x	x	x	x	x
Study Intervention											
Randomization		(x) 									
In-Patient Admission		(x) 									
Study Drug Administration	x										
Study Procedure											
ECG	x										
Inhalation-related Events (+ Infusion-related in Group 2D )	x	x	x	x	x						
Adverse Events		x	x	x	x	x	x	x	x	x	x
General Physical	x										
Directed Physical 	x	x	x	x	x	x	x	x	x	x	x
Vital Signs 	x	x 	x	x	x	x	x	x	x	x	x
Weight	x								x		x
Height	x										
Pregnancy counseling	x										
Pregnancy testing in women of childbearing potential	x	x 						x	x	x	x
WHO R&D Clinical Progression Scale	x	x	x	x	x	x	x	x	x	x	x
Biosamples											
Virology screening labs  (Local lab)	x										
Safety lab  (Local lab)	x	x	x	x		x		x	x	x	x
Coagulation parameters (INR, PTT) (Local lab)	x										
SARS-CoV-2 antibody serology (Local lab)	x	x									
Urinalysis  (Local lab) ( Groups 2A-2C only )	x					x		x			x
PK samples (Central lab)	x 	x	x	x	x	x	x	x	x	x	x
Nasopharyngeal SARS-CoV-2 swab (Central lab)	x	x	x	x	x	x	x	x	x	x	x
Oropharyngeal SARS-CoV-2 swab (Central lab)	x	x	x	x	x	x	x	x	x	x	x
Naso- or Oropharyngeal SARS-CoV-2 swab (Local lab)	x 										
Oropharyngeal SARS-CoV-2 swab (Local lab)		(x  )									
Anti-DZIF-10c antibody (ADA) assay sample (Central lab)	x							x	x	x	x
Research lab (PBMCs) (Central lab)		x							x		x

1. In **Group 2D**, screening and infusion procedure may be performed on the same day. SARS-CoV-2 swabs for central lab PCR are mandatory to be obtained prior to the infusion.
2. Trial visits on day 5 and day 10 are considered optional pending local capacity for quarantine visits.
3. Randomization in **Group 2D** only.
4. In-patient admission required in **Groups 2A-2C**, and at the discretion of the investigator in **Group 2D**.

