6.7 BASELINE, TIME WINDOWS AND CALCULATED VISITS

As a general rule, the last assessment / measurement observed prior to start of trial medication will be assigned to baseline. Note that for some trial procedures (e.g., body weight, vital signs, laboratory tests) this may be the value measured on the same day trial medication was started. In these cases, it will be assumed that the measurements were taken prior to the intake of any study medication (if the measurement time was not captured). If no further data available, this can also be the last screening assessment. For viral load and pulmonary function test related

data it is paramount that the sample is taken prior to drug administration, and for these procedures time of sampling will be taken into consideration and compared to the time of drug intake.

Furthermore, for assessments of viral load data for the first 7 days after drug administration which require grouping to timepoints (e.g., descriptive statistics by timepoint, MMRM), the following will be done. Measurements for baseline (day 1) and days 2, 4, 6 and 8 will be included, where the measurement for day 6 is optional. The following time windows are allowed.

- The measurements for baseline and for day 2 must be taken exactly on the respective day. There is no time window.
- If there is no measurement on day 4, it will be replaced by a measurement on day 3 or day 5 with a preference for day 3.
- If there is no measurement on day 8, it will be replaced by a measurement on day 7.

If the optional measurement on day 6 is missing, it will be replaced by the value on day 5 or day 7 if these values have not been assigned to days 4 and 8, respectively. The measurement for day 5 will be preferred over day 7 if both values are available.

Additionally, for assessments of viral load data for the first 14 or 28 days after drug administration which require grouping to timepoints (e.g., MMRM), the following time windows apply. These analyses windows are non-overlapping and cover the whole trial period by using the middle between each scheduled visit.

- If there are no measurement on days 7 and 8, the day 8 measurement will be replaced by the earliest measurement up to day 11.
- If there is no measurement on day 15, it will be replaced by the closest measurement taken between day 12 and day 18.
- If there is no measurement on day 22, it will be replaced by the closest measurement taken between day 19 and day 25.

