7.5.2.2.2 The frequency and magnitude of anti-drug antibodies targeting DZIF-10c

The same assessments will be performed as described in [Section 7.5.2.1.2](#).

This endpoint will be evaluated on the subject set TS.

7.5.2.2.3 SARS-CoV-2 RNA shedding in nasopharyngeal swabs determined by qRT-PCR in SARS-CoV-2-infected individuals

All evaluations for the first 7 days after drug administration will be done on the mITT set and will take data into consideration based on the time window around the corresponding visit as defined in [Section 6.7](#). The latest day to be taken into account is 7 days after drug administration. The evaluations for the later time points will be based on all subjects in the subject set TS who have at least a baseline value and a second measurement in the respective time period of viral RNA shedding in NP swabs by qRT-PCR.

Absolute viral load in SARS-CoV-2-infected individuals, as well as absolute and relative changes from baseline, will be summarised descriptively for each assessment time point and plotted by treatment arm and listed.

Time-weighted average change in viral load

The evaluation of viral load will be done by a time-weighted average change in \log_{10} viral load from baseline, defined by:

$$\frac{\sum_{i=a}^{b-1} \{0.5 * (Y_i + Y_{i+1}) * (t_{i+1} - t_i)\}}{(t_b - t_a)}$$

where

- Y_i = change from baseline in \log_{10} viral load at visit i
- t = time at the specified time point (the actual study day)
- a = baseline assessment at day 1
- b = last assessment at or prior to the threshold day (7 days after drug intake)

A parametric analysis of covariance (ANCOVA) model with corresponding baseline viral load and antibody status will be used. Adjusted means and 95% confidence intervals (CIs) will be provided. Missing values will not be imputed and since a linear trajectory on the log scale is expected, the normalisation by the denominator assures comparability of the values if t_b is different between patients.

Ratios between means (DZIF-10c vs placebo) will be calculated for each treatment arm separately for the respective time period. These calculations will be based on the mean time-weighted average change in viral load based on the ANCOVA model. CIs for the ratios will be reported for which the Delta method (Taylor method) will be used to calculate the variance of the ratios.

Mixed effect Model for Repeated Measures (MMRM)

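### The later viral-load windows in SAP 6.7 follow the healthy-volunteer calendar (day 22 present, day 11 absent); separately, the 7-day analyses exclude day-7 swabs taken on the permitted later day

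*SAP*

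**What the plan says.** SAP 4.2 relabels the dosing day as day 1, so a SAP day is the protocol day plus one. Below, D7 means protocol day 7, and 'SAP day 8' is the same day.

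For analyses of the first 14 or 28 days that need swabs grouped to timepoints, SAP 6.7 names days 8, 15, 22 and 29. It adds days 57 and 91 for descriptive statistics. It says the windows are set "by using the middle between each scheduled visit", and for day 22: "If there is no measurement on day 22, it will be replaced by the closest measurement taken between day 19 and day 25". If days 7 and 8 are both empty, "the day 8 measurement will be replaced by the earliest measurement up to day 11".

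For the 7-day analyses, SAP 6.7 lets a missing day 8 be replaced by day 7 only. SAP 7.5.2.2.3 adds: "The latest day to be taken into account is 7 days after drug administration".

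Protocol Appendix II B, for infected participants, ends its day row with "D10 2 D 14 D 28 D 56 D 90" (the lone 2 is a footnote marker). There is a D10 visit and no D21. Its tolerance row reads "Visit Window (+/- days) - - - 1 1 1 1 2 3 4 7". The footnote says: "Trial visits on day 5 and day 10 are considered optional pending local capacity for quarantine visits". Appendix II A, for healthy volunteers, ends with "D 14 D 21 D 28 D 56 D 90". It has D21 and no D10.

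**The concern.** The analysis windows should mirror the visits of the people whose swabs are analysed. Healthy volunteers have local-laboratory swabs only, and none at D21, so they contribute no viral-load series. A timepoint that infected participants never attend, together with a scheduled swab that has no timepoint, means the grouped outputs do not match the data collected. Those outputs are the 14- and 28-day mixed models (MMRM) and the by-timepoint summaries.

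The handling of a late D7 swab is a second, independent matter. Protocol 8.1.1 and 8.1.4 define the mITT population and the time-weighted average by the day 7 visit, which may take place on D8. The SAP counts seven elapsed days instead. A compliant swab can therefore be left out of the 7-day analyses and kept in the longer ones, so that 'day 8' means different data in different models. The SAP's example code (9.2.1.2) labels 7 days the primary MMRM analysis, and the 7-day results feed the second interim analysis.

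**Working it through.** **1. Reproduce the SAP's cut points.** Take the midpoint of neighbouring visits, in SAP days.

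- Healthy calendar (8, 15, 22, 29, 57, 91): (8+15)/2 = 11.5, (15+22)/2 = 18.5, (22+29)/2 = 25.5, (29+57)/2 = 43, (57+91)/2 = 74. The cuts are 11/12, 18/19, 25/26, 43/44 and 74/75, all as in SAP 6.7. The outer end of day 91 is not fixed by a midpoint.
- Infected calendar (8, 11, 15, 29, 57, 91): (8+11)/2 = 9.5, (11+15)/2 = 13, (15+29)/2 = 22, then 43 and 74. The cuts are 9/10, 13/14, 22/23, 43/44 and 74/75, with no day 22.
- Infected calendar with the optional D10 left out (8, 15, 29, 57, 91): 11.5, 22, 43, 74. There is still no day 22.

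**2. Place every permitted infected swab day in the SAP windows.**

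| Visit and tolerance | SAP days | 7-day analyses | 14-/28-day grouped analyses |
|---|---|---|---|
| D7 ±1 | 7-9 | 7 and 8 usable; 9 excluded | 9 becomes day 8 if 7 and 8 are empty |
| D10 ±1 | 10-12 | after the cut-off | 10 or 11 becomes day 8 only if 7 and 8 are empty and it is the earliest swab, otherwise unassigned; 12 falls in the day-15 window |
| D14 ±2 | 13-17 | after the cut-off | day-15 window |
| D28 ±3 | 26-32 | after the cut-off | day-29 window |

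No permitted day lies in 19-25, so only an out-of-window or unscheduled swab can supply a day-22 value. D5 is as optional as D10, yet SAP 6.7 gives it its own timepoint (day 6).

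**3. Effect of a stray day-22 value on the 28-day MMRM.** Post-baseline levels without it are days 2, 4, 6, 8, 15 and 29, so k = 6. An unstructured covariance has k(k+1)/2 parameters: 6×7/2 = 21. With a day-22 level, 7×8/2 = 28.

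**4. Effect of relabelling.** A day-11 swab used as day 8 is misdated by 3 days. The documents give no rate of decline. At an assumed 0.2 to 0.5 log10 per day, the error is 3×0.2 = 0.6 to 3×0.5 = 1.5 log10 for that value.

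**5. Effect of losing a late D7 swab on the 7-day time-weighted average.** SAP 7.5.2.2.3 expects a linear trajectory on the log scale. Write the change as Y = s·t, with t in days since dosing. The average up to the last swab at t_b is (s·t_b²/2)/t_b = s·t_b/2.

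- Last swab on D7: 3.5s.
- D7 swab taken on D8 and excluded, no D5 swab, last swab on D3: 1.5s. The ratio is 1.5/3.5 = 3/7 = 43%.
- Same participant with the D8 swab admitted: 4s. The ratio is 4/3.5 = 8/7 = 114%.

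Under the SAP's own linear assumption the average is proportional to t_b. Dividing by elapsed time therefore does not make participants with different last days comparable, contrary to what that section says.

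**The case against.** The case against giving this much weight is strong on several points, and most of it stands.

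- A reader might infer that all D10 swabs, up to 60 in Group 2D, go unused. The documents do not support that. The time-weighted average uses the actual study day, so D10 swabs enter the 14- and 28-day averages. Viral load is also listed. The loss is confined to grouped outputs, for a visit the protocol makes optional.
- A reader might infer that late D7 swabs are lost throughout, because of the wrong calendar. Neither part holds. SAP 6.7 keeps day 9 as day 8 in the longer analyses. D7 has a ±1 tolerance in both appendices, so the exclusion comes from the 7-day cut-off. Such a participant normally stays in the mITT set through a D1 or D3 swab.
- A reader might infer that the day-22 level will break the MMRM. An empty level contributes nothing. With stray values, SAP 7.5.2.2.3 already gives a sequence of simpler covariance structures if the model does not converge.
- Nothing in the documents shows that D10 lies in the steepest part of the decline.
- The primary endpoint is adverse events. Viral load is secondary, with no formal testing and only nominal p-values.

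What remains is that the SAP departs from its own midpoint rule. SAP 4.2 explains the shift by one day, and SAP 4.3 says slight differences in study day are deliberate. Neither explains an added visit or an omitted one.

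**Conclusion.** The point holds within these limits. From day 8 on, the windows are those of the healthy-volunteer calendar. Day 22 is a visit infected participants do not have, and the D10 swab is unassigned, stands in for day 8, or falls to day 15 if taken on SAP day 12. This affects the grouped analyses only.

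Separately, the 7-day analyses exclude a protocol-compliant swab that the longer models accept. The 43% figure is one participant's worst case. It requires a D7 swab taken on D8, no D5 swab, a D3 swab on the exact day and a linear trajectory. It is not an estimate of bias in an arm mean, because the documents do not say how often this combination would occur. The 0.6 to 1.5 log10 range rests on an assumed slope and also applies to single values.

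No primary result depends on this. It is a modest correction to secondary, exploratory analyses, not something that must be fixed before the plan can be used.

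**What to change.** Rebuild the later windows in SAP 6.7 on Appendix II B, following the protocol's visit tolerances (SAP days):

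- day 8 = days 7-9;
- day 11 = days 10-12 (new);
- day 15 = days 13-17;
- day 29 = days 26-32;
- delete day 22.

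Within a window, take the swab closest to the target day, and state a tie rule for day 7 against day 9. Keep the present precedence, under which swabs on days 5 and 7 go to days 4 and 8 before day 6. List swabs outside the windows, and keep them in the time-weighted average by actual day.

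Define the 7-, 14- and 28-day periods as ending at the day 7, 14 and 28 visits, tolerances included. This is needed because SAP 7.5.2.2.3 bars data after each cut-off while the 6.7 windows run past it: the day-15 window extends to day 18. Then bring the mITT definition (SAP 6.3), SAP 6.7, both cut-off statements in SAP 7.5.2.2.3 and deviation code F2 (SAP 6.2) into agreement. F2 now allows day 8 ±2 against the protocol's ±1.

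The cost is SAP text and derivation code, best settled before unblinded data are seen. There are two downsides. The 7-day analysis would admit swabs from the eighth day after dosing (114% against 43% in the working above). The optional day-11 level also takes the 28-day unstructured covariance from 21 to 28 parameters, for which the existing fallback sequence provides.

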7. PLANNED ANALYSIS

Planned analyses can be categorized based on:

- The study period for which they are performed:
 - Phase I dose escalation and phase IIa expansion cohort.
- The study population for which they are performed:
 - Healthy volunteers or SARS-CoV-2-infected individuals.

Unless specified otherwise, analyses for the phase I dose escalation part and the phase IIa expansion cohort part will be identical. The same will hold true for evaluations including healthy volunteers and SARS-CoV-2-infected individuals.

For End-Of-Text tables, the set of summary statistics is: N / Mean / SD / Min / Q1 / Median / Q3 / Max. In descriptive statistics tables, mean, sd and median will be rounded to one additional digit than the raw data. In case extreme data outside of the expected range are observed, other percentiles may be presented additionally in the phase IIa outputs.

Tabulations of frequencies for categorical data will include all categories depicted in the eCRF and will display the number of observations in a category as well as the percentage (%) relative to the respective treatment group (unless otherwise specified, all subjects in the respective subject set whether they have non-missing values or not). Percentages will be rounded to one decimal place. The category missing will be displayed only if there are actually missing values.

All evaluations are exploratory in nature and p-values will be presented where appropriate.

7.1 DEMOGRAPHIC AND OTHER BASELINE CHARACTERISTICS

A table in the CTR will present the number of subjects screened, entered (only applicable for subjects in the phase I part of the study)/randomised (only applicable for subjects in the phase IIa part of the study) and treated. The number of subjects prematurely discontinuing their study treatment / study participation will be shown with the reasons for discontinuation. The number and percent of subjects completing trial visits and the number of subjects ongoing will also be presented. Please note there will only be ongoing subjects at the time the interim analyses take place; at the time point when the final analysis will take place there will not be any more ongoing subjects in this trial. Where percentages are shown, the denominator will be the number of subjects treated in each cohort, separately for each study part.

Descriptive statistics, as well as frequency counts, will be provided for all demographic and baseline characteristics depicted in [Section 5.4.1](#). The CTR tables will show the relevant descriptive statistics (number and percent within categories; other descriptive statistics for continuous variables) by cohort and study part.

Only descriptive statistics are planned for this section of the report.

7.2 CONCOMITANT DISEASES AND MEDICATION

Only descriptive statistics are planned for this section of the report.

7.2.1 Baseline conditions and relevant medical history

The baseline conditions will be included as coded items using the current Medical Dictionary for Regulatory Activities (MedDRA) version in use at UKK at the time of database lock. They will be summarised by MedDRA primary system organ class (SOC) and Preferred Term. The CTR table will show the counts of subjects with a baseline condition in each SOC present (SOC sorted by standard European Medicines Agency (EMA) order) and then the conditions (preferred terms) under that SOC in descending order of overall prevalence. This summary will be produced on all subjects, separate for each study period.

The relevant medical history will be summarised. In SARS-CoV-2 infected subjects particular focus will be to baseline disease assessment and contributing factors to a potentially more severe course of SARS-CoV-2.

7.2.2 Concomitant therapies

The following categories of concomitant therapies have been created:

- Previous therapies
 - Defined as treatments with an end date before trial drug intake. As per eCRF, the last four weeks before drug intake are collected.
- Baseline therapies
 - Defined as treatments with a start date before trial drug intake and taken after or on the day of the trial drug intake.
- On-treatment concomitant therapies
 - Defined as treatments with a start date after or on the day of trial drug intake and before or on the last day of the residual effect period (for details, please see [Section 6.1](#)).
- Post-study drug discontinuation therapies
 - Defined as treatments with a start date after the end of the residual effect period (for details, please see [Section 6.1](#)).

The analysis of concomitant therapies will be based on the following groupings of the aforementioned categories of concomitant therapies:

- Previous therapies
- Baseline therapies
- On-treatment concomitant therapies
- Baseline and on-treatment concomitant therapies
- All concomitant therapies (including baseline therapies, on-treatment concomitant therapies and post-study drug discontinuation therapies)
- Post-study drug discontinuation therapies

Concomitant therapies will be described separately for both the phase I and the phase IIa part of the trial.

Table 7.2.2: 1 Table 7.2.2: 1 summarises the concomitant therapy outputs which will be provided for both trial phases. Summaries by WHO-DD ATC and preferred name (PN) will use the ATC3 code, and will be sorted by alphabetical ATC class and decreasing frequency of PN based on the overall number of subjects taking them within ATC class. Summaries by SDGs will be sorted by alphabetical SDG and decreasing frequency of PN based on the overall number of subjects taking them within SDG. SDGs can be found in [Section 9.3](#).

Table 7.2.2: 1 Concomitant therapy outputs.

	By ATC and PN		By SDGs and PN	
	Phase I dose escalation	Phase IIa expansion cohort	Phase I dose escalation	Phase IIa expansion cohort
Previous therapies	Listing	Listing	Listing	Listing
Baseline therapies	Table + listing	Table + listing	Table + listing	Table + listing
On-treatment concomitant therapies	Table + listing	Table + listing	Table + listing	Table + listing
Post-study drug discontinuation therapies	Table + listing	Table + listing	Table + listing	Table + listing

